We have established a multidisciplinary group of radiation oncologists, urologists, geneticists and engineers that is uniquely positioned to address this knowledge gap about the importance of the BRCA mutation and risk of prostate cancer. Our group has developed the Yale School of Medicine Fusion Prostate Biopsy Program. This program uses cutting-edge multiparametric magnetic resonance imaging (MRI) to identify previously invisible lesions in the prostate. The office-based Artemis platform (Eigen, Grass Valley CA) then “fuses” these images with 3D ultrasound to achieve more precise and accurate prostate biopsies, allowing for better clinical staging with a single biopsy. The Yale Fusion Prostate Biopsy Program has dramatically improved prostate cancer detection to more than 60%, almost twice that of the current standard of care. Through the Yale Cancer Center Genetic Counseling program, which provides genetic counseling and testing to people at increased risk for hereditary cancer, we have an established cohort of families with known genetic mutations including BRCA2.

Our study, by combining the Fusion Prostate Biopsy Program and the Genetic Counseling program to perform highly sensitive prostate biopsies in a population of BRCA2 mutation carriers, is a novel approach to accurately determine the risk of prostate cancer, adverse pathologic features and abnormal MRI findings among BRCA2 mutation carriers. While it is beyond the scope of this pilot grant, we believe that early identification of men with higher risk disease should allow for more rapid treatment and a higher likelihood of cure. We hypothesize that the BRCA-2 mutation is associated with a higher risk of prostate cancer incidence, worse grade, and abnormal MRI findings compared to patients without this mutation. To address these important questions, our specific aims are:

1. To prospectively determine the incidence of prostate cancer in BRCA2 mutation carriers.
2. To investigate different characteristics of MRI-detected prostate lesions.
3. To compare pathologic and clinical findings to clinically matched controls using the same sensitive MRI-based biopsy technique.

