Typical clinical workflow for an Artemis MR-US fusion biopsy includes a pre-procedure MRI followed by a 12-core transrectal-ultrasound (TRUS) guided biopsy (Figure 1,2). The ultrasound transducer is fixed with a needle guide, and the biopsy needle is then guided to specific regions in the prostate gland for systematic sampling of the gland. If any areas suspicious for cancer (labeled regions of interest (ROIs)) are identified in the MRI, they are outlined using specialized software, and the target is visible on the Artemis device. Targeted biopsies will be taken from each ROI to rule out cancer in these suspicious areas.

4. **Genetic Testing** N/A

5. **Subject Population:** Provide a detailed description of the types of human subjects who will be recruited into this study.

Men \geq 30 years of age with known BRCA2 mutation and able to give informed consent.

6. **Subject classification:** Check off all classifications of subjects that will be specifically recruited for enrollment in the research project. Will subjects who may require additional safeguards or other considerations be enrolled in the study? If so, identify the population of subjects requiring special safeguards and provide a justification for their involvement.

 Children	 Healthy	 Fetal material, placenta, or dead fetus
 Non-English Speaking	 Prisoners	 Economically disadvantaged persons
 Decisionally Impaired	 Employees	 Pregnant women and/or fetuses
 Yale Students	 Females of childbearing potential	

NOTE: Is this research proposal designed to enroll children who are wards of the state as potential subjects? Yes No (If yes, see Instructions section VII #4 for further requirements)

7. **Inclusion/Exclusion Criteria:** What are the criteria used to determine subject inclusion or exclusion?

All men \geq 30 years of age with at least a ten-year life expectancy, a known BRCA2 mutation, ability to have an MRI, and able to give informed consent will be approached to participate in the study. If a man has received or is currently receiving treatment for prostate cancer he will be excluded from the study.

8. How will **eligibility** be determined, and by whom?

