11. Data and Safety Monitoring Plan: Include an appropriate Data and Safety Monitoring Plan (DSMP) based on the investigator's risk assessment stated below. (Note: the HIC will make the final determination of the risk to subjects.) For more information, see the Instructions, page 24.

a. What is the investigator's assessment of the overall risk level for subjects participating in this study?

- Moderate risk: participants will be offered the standard of care fusion targeted prostate biopsy that is performed at Yale and offered to other patients at risk for prostate cancer. Some participants, however, would not have received a biopsy if not participating in the study.

1. Personnel responsible for the safety review and its frequency:

The principal investigator will be responsible for monitoring the data, assuring protocol compliance, and conducting the safety reviews at the specified frequency which must be conducted at a minimum of every 6 months (including when reapproval of the protocol is sought). During the review process, the principal investigator (monitor) will evaluate whether the study should continue unchanged, require modification/amendment, or close to enrollment. Either the principal investigator, the IRB or the Yale Cancer Center Data and Safety Monitoring Committee (DSMC) have the authority to stop or suspend the study or require modifications.

2. The risks associated with the current study are deemed moderate for the following reasons: (choose those that apply)

1. We do not view the risks associated with the prostate biopsy as minimal given the alternative is no biopsy.
2. Given the now established safety and validity of the current biopsy procedure in our prior work, we do not view the proposed studies as high risk.

Although we have assessed the proposed study as one of moderate risk, the potential exists for anticipated and/or unanticipated adverse events, serious or otherwise, to occur since it is not possible to predict with certainty the absolute risk in any given individual or in advance of first-hand experience with the proposed study methods. Therefore, we provide a plan for monitoring the data and safety of the proposed study as follows:

3. Attribution of Adverse Events:

Adverse events will be monitored for each subject participating in the study and attributed to the study procedures / design by the principal investigator [name] according to the following categories:

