7. Plan for reporting adverse events to co-investigators on the study, as appropriate the protocol's research monitor(s), e.g Yale Cancer Center Data and Safety Monitoring Committee (DSMC), Protocol Review Committee (PRC), DSMBs, study sponsors, funding and regulatory agencies, and regulatory and decision-making bodies.

For the current study, the following individuals, funding, and/or regulatory agencies will be notified (choose those that apply):

All Co-Investigators listed on the protocol.

Yale Cancer Center Data and Safety Monitoring Committee (DSMC)

National Institutes of Health

Food and Drug Administration (Physician-Sponsored IND # _____)

Medical Research Foundation (Grant _____)

The principal investigator [name] will conduct a review of all adverse events upon completion of every study subject. The principal investigator will evaluate the frequency and

severity of the adverse events and determine if modifications to the protocol or consent form are required.

d. For multi-site studies for which the Yale PI serves as the lead investigator: N/A

12. Statistical Considerations: Describe the statistical analyses that support the study design.

This is a screening study to establish the incidence of prostate cancer in a high-risk population since it is not currently known. There is an estimated 4.6-23 fold increased risk of prostate cancer, especially in men < 58 years of age with a BRCA2 mutation. Typically, prostate cancer detection in normal risk men correlates directly with age and ranges between 0.01 and 6.5% for men in their 30s-60s (CDC website). Given these parameters, we plan initial evaluation of 100 men.

SECTION VI: RESEARCH INVOLVING DRUGS, BIOLOGICS, RADIOTRACERS, PLACEBOS AND DEVICES

N/A

SECTION VII: RECRUITMENT/CONSENT AND ASSENT PROCEDURES

1. Targeted Enrollment: Give the number of subjects:

- a. targeted for enrollment at Yale for this protocol 100
- b. If this is a multi-site study, give the total number of subjects targeted across all sites

2. Indicate recruitment methods below. Attach copies of any recruitment materials that will be used.

 Flyers	 Internet/Web Postings	 Radio
 Posters	 Mass E-mail Solicitation	 Telephone

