All geographic subdivisions smaller than a State, including: street address, city, county, precinct, zip codes and their equivalent geocodes, except for the initial three digits of a zip code if, according to the current publicly-available data from the Bureau of the Census: (1) the geographic unit formed by combining all zip codes with the same three initial digits contains more than 20,000 people, and (2) the initial three digits of a zip code for all such geographic units containing 20,000 or fewer people is changed to 000.

Telephone numbers

Fax numbers

E-mail addresses

Social Security numbers

Medical record numbers

Health plan beneficiary numbers

Account numbers

All elements of dates (except year) for dates related to an individual, including: birth date, admission date, discharge date, date of death, all ages over 89 and all elements of dates (including year) indicative of such age, except that such ages and elements may be aggregated into a single category of age 90 or older

Certificate/license numbers

Vehicle identifiers and serial numbers, including license plate numbers

Device identifiers and serial numbers

Web Universal Resource Locators (URLs)

Internet Protocol (IP) address numbers

Biometric identifiers, including finger and voice prints

Full face photographic images and any comparable images

Any other unique identifying numbers, characteristics, or codes

5.

Assessment of Current Health Provider Relationship for HIPAA Consideration:

Does the Investigator or any member of the research team have a direct existing clinical relationship with any potential subject?

Yes, all subjects
 Yes, some of the subjects
 No

If yes, describe the nature of this relationship.

[name] could potentially see some of these patients while they are undergoing their standard of care prostate cancer treatment.

6. **Request for waiver of HIPAA authorization:** (When requesting a waiver of HIPAA Authorization for either the entire study, or for recruitment purposes only. Note: if you are collecting PHI as part of a phone or email screen, you must request a HIPAA waiver for recruitment purposes.)

Choose one: For entire study: _____ For recruitment purposes only: _____

- i. Describe why it would be impracticable to obtain the subject's authorization for use/disclosure of this data;

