- ii. If requesting a waiver of **signed** authorization, describe why it would be impracticable to obtain the subject's signed authorization for use/disclosure of this data;

By signing this protocol application, the investigator assures that the protected health information for which a Waiver of Authorization has been requested will not be reused or disclosed to any person or entity other than those listed in this application, except as required by law, for authorized oversight of this research study, or as specifically approved for use in another study by an IRB.

Researchers are reminded that unauthorized disclosures of PHI to individuals outside of the Yale HIPAA-Covered entity must be accounted for in the “accounting for disclosures log”, by subject name, purpose, date, recipients, and a description of information provided. Logs are to be forwarded to the Deputy HIPAA Privacy Officer.

7. **Required HIPAA Authorization:** If the research involves the creation, use or disclosure of protected health information (PHI), separate subject authorization is required under the HIPAA Privacy Rule. Indicate which of the following forms are being provided:

Compound Consent and Authorization form
 HIPAA Research Authorization Form

8. **Consent Personnel:** List the names of all members of the research team who will be obtaining consent/assent.

[name]

9. Process of Consent/Assent: Describe the setting and conditions under which consent/assent will be obtained, including parental permission or surrogate permission and the steps taken to ensure subjects' independent decision-making.

Prior to screening for prostate cancer patients will have an office visit as part of standard clinical care to discuss the risks and benefits of prostate cancer screening. During this visit, if they are interested in being screened for prostate cancer and meet eligibility criteria the study will be described and if patients are interested in participating they will be provided a study information sheet and asked to sign consent. Only patients that can provide written informed consent will be enrolled in this study, and if there is any doubt subjects will not be enrolled. Information sheets will also be available to patients as part of the Yale Cancer Genetic Counseling Program.

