Requesting a waiver of signed consent for the Entire Study (Note that an information sheet may be required.)

If requesting a waiver of signed consent, please address the following:

a. Would the signed consent form be the only record linking the subject and the research?

Yes No

b. Does a breach of confidentiality constitute the principal risk to subjects?

Yes No

OR

c. Does the research pose greater than minimal risk? Yes ***If you answered yes, stop. A waiver cannot be granted.*** No

AND

d. Does the research include any activities that would require signed consent in a non-research context? Yes No

B. Full waiver of consent: (No consent from subjects will be obtained for the activity.)

Requesting a waiver of consent for Recruitment/Screening only

a. Does the research activity pose greater than minimal risk to subjects?

Yes ***If you answered yes, stop. A waiver cannot be granted.*** Please note:

Recruitment/screening is generally a minimal risk research activity

No

b. Will the waiver adversely affect subjects' rights and welfare? Yes No

c. Why would the research be impracticable to conduct without the waiver?

d. Where appropriate, how will pertinent information be returned to, or shared with subjects at a later date?

Requesting a full waiver of consent for the Entire Study (Note: If PHI is collected, information here must match Section VII, question 6.)

If requesting a full waiver of consent, please address the following:

- a. Does the research pose greater than minimal risk to subjects?
 Yes ***If you answered yes, stop. A waiver cannot be granted.***
 No
- b. Will the waiver adversely affect subjects' rights and welfare? Yes No
- c. Why would the research be impracticable to conduct without the waiver?
- d. Where appropriate, how will pertinent information be returned to, or shared with subjects at a later date?

SECTION VIII: PROTECTION OF RESEARCH SUBJECTS

Confidentiality & Security of Data:

- a. What protected health information (medical information along with the HIPAA identifiers) about subjects will be collected and used for the research?
- b. Subject Name, date of birth, and Medical Record number as well as clinical imaging, pathologic and staging information will be collected.
- c. How will the research data be collected, recorded and stored?

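### Aim 3 and the comparative hypothesis need men without the mutation, but the protocol enrols only BRCA2 carriers and provides no control group, data route or comparative analysis

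*Combined protocol and SAP*

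**What the plan says.** The comparison is promised in Section V.2 (Background). The hypothesis is that the mutation goes with a higher incidence of prostate cancer, "worse grade, and abnormal MRI findings compared to patients without this mutation". Specific aim 3 is "To compare pathologic and clinical findings to clinically matched controls using the same sensitive MRI-based biopsy technique".

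The operative sections describe one group:

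- V.1 (Statement of Purpose) lists a single aim, the incidence of prostate cancer in men with the mutation.
- V.3 (Research Plan) describes a screening cohort of carriers, all of whom have PSA, examination, MRI and fusion biopsy. Under standard care, normal-risk men go on to MRI and biopsy only if PSA or examination is abnormal.
- V.4 marks genetic testing as not applicable.
- V.5 defines the population as men of at least "30 years of age with known BRCA2 mutation and able to give informed consent". V.7 repeats the mutation requirement, and V.8 has it confirmed from the BRCA2 registry.
- V.12 addresses incidence in this high-risk group and arrives at 100 men. VII.1 gives the same number: "targeted for enrollment at Yale for this protocol 100".
- VII.3 recruits known carriers and newly tested carriers through the genetic counseling program, and asks female carriers to invite male relatives who carry the mutation.
- VII.6 (waiver of HIPAA authorization) reads "Choose one: For entire study", with both options and both justifications left blank.
- VII.9 states "Only patients that can provide written informed consent will be enrolled in this study".

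**The concern.** A hypothesis about a difference needs data from both groups. Here the second group has no entry criteria, source, number, matching factors, access route or analysis. The gap goes beyond missing detail, because the eligibility rule excludes the men that aim 3 requires.

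The practical risk is an improvised comparator, chosen after the carrier results are known. Two are close at hand, and they would probably mislead in opposite directions. The V.12 population rates come from men who were not all biopsied, so setting universally biopsied carriers beside them would tend to exaggerate the carrier excess. The fusion program's detection figure of more than 60% (V.2), if it comes from men referred after abnormal screening, could hide or reverse a true excess.

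**Working it through.** **1. The promise against the provision.**

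| Needed for aim 3 | Where it would stand | What is there |
|---|---|---|
| Men without the mutation | V.5, V.7 | Known BRCA2 mutation required |
| Confirmation of mutation-negative status | V.4, V.8 | Testing not applicable; only carrier status is checked |
| A source of controls | V.3, VII.3 | Carriers and carrier relatives |
| A number of controls | V.12, VII.1 | 100 men, carriers under V.7 |
| Access to control data | VII.6, VII.13 | VII.6 blank; VII.13 selections not legible in the text available |
| An analysis | V.12 | None |

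Planned controls = 0, so neither a difference nor its power can be computed.

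**2. The plan's own figure.** V.12 gives normal-risk detection of 0.01 to 6.5% (read here as 0.01% to 6.5%), a 4.6 to 23 fold increase, and N = 100. It states no alpha, power, precision target or formula, so 100 cannot be derived from it.

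- Implied carrier rates: 6.5% × 4.6 = 29.9%; 6.5% × 23 = 149.5%, which is impossible; 0.01% × 4.6 = 0.046%; 0.01% × 23 = 0.23%.
- One-sample test, 6.5% vs 29.9%, n = [(z_α√(p0(1−p0)) + z_β√(p1(1−p1)))/(p1−p0)]². At two-sided 5% and 80% power this is [(1.96 × 0.2465 + 0.8416 × 0.4578)/0.234]² = 13.8, so 14. One- or two-sided, at 80% or 90% power, the range is 12 to 21.
- Two-sample test, same rates: 33 to 56 per group, or 41 to 64 with continuity correction. The two-sided, 80% power, corrected version gives 50 per group, or 100 in total. That would mean 50 carriers and 50 controls, whereas the protocol's 100 are all carriers.
- A half-width of 10 points at p = 0.5 needs 1.96² × 0.25/0.01 = 96.04, so 97. No such target is stated.

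**3. What 100 carriers deliver.** Exact (Clopper-Pearson) 95% intervals for the detection proportion are:

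- 0 cancers: 0 to 3.6%
- 10 cancers: 4.9% to 17.6%
- 30 cancers: 21.2% to 40.0%

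This is a usable one-sample result, but it contains no information on non-carriers.

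**4. What a retained comparison would face.** The only detection figure in the documents for fusion-biopsied men is more than 60%. Taking 60% in both groups, an unmatched analysis and assumed control numbers, the 95% half-width for a difference is 1.96√[p(1−p)(1/n1 + 1/n2)]:

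- 100 carriers vs 100 controls: 1.96√(0.24 × 0.020) = 13.6 points
- 100 vs 200: 1.96√(0.24 × 0.015) = 11.8 points
- 50 vs 100, if only half the carriers had an abnormal PSA or examination (an assumed share): 1.96√(0.24 × 0.030) = 16.6 points

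Power at two-sided 5% with 100 carriers, all rates assumed: for 60% vs 70%, 32% with 100 controls and 39% with 200; for 60% vs 80%, 88% and 95%.

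**The case against.** The best defence is that V.1, the formal purpose, lists incidence alone, and that the design and V.12 agree with it. On that view the comparison is background ambition and nothing primary is lost. The second half stands: the carrier estimate is unaffected. The first does not, because V.2 sets out aim 3 among the study's specific aims and states the hypothesis outright.

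A reader might go further and infer that the consent and privacy rules bar every non-carrier record. The chain would be "Only patients that can provide written informed consent will be enrolled in this study" in VII.9, the blank VII.6, the rating in V.11 ("Moderate risk: participants will be offered the standard of care fusion targeted prostate biopsy") and the form's rule in VII.13 for research above minimal risk: "If you answered yes, stop. A waiver cannot be granted". The documents do not support that:

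- The VII.9 sentence concerns the consent of men being enrolled, not who may supply comparison data.
- The VII.13 selections cannot be read.
- The waiver rule addresses this study and its recruitment, not a record review under separate approval.
- VII.7 requires authorization only where protected health information is involved.

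The blank VII.6 suggests that no waiver was requested here. The protocol therefore provides no route for control data; it does not prohibit one.

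A reader might also suppose that men already biopsied in the fusion program are ready-made controls. Nothing says their BRCA2 status is known, and under V.3 normal-risk men reach biopsy after an abnormal PSA or examination, while every enrolled carrier is biopsied.

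**Conclusion.** The concern holds in this form: the protocol commits to a comparison for which it plans zero controls and no analysis. Followed as written, it can report a detection proportion and the MRI and pathologic findings in carriers. It cannot say whether incidence, grade or MRI findings are worse than in men without the mutation. The population rates in V.12 do not fill the gap, since aim 3 specifies one biopsy technique for both groups.

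This should be corrected, but it does not undermine the aim in V.1. The conclusion rests on V.2, V.5, V.7, V.12 and VII.1 and needs no assumed rate. The half-widths and power for a retained comparison are illustrations only.

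**What to change.** **Preferred.** Delete aim 3 and the comparative part of the hypothesis from V.2. Limit objectives and conclusions to the detection proportion, with its exact interval, and the MRI and pathologic description in carriers. This is consistent with V.1 and costs one text amendment. What is lost is a comparative claim that the design cannot support.

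**If the sponsor keeps the comparison**, add a control component to V.5, V.7, V.12 and VII.1, counted apart from the 100 carriers, that states:

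- the source and number of controls and the matching factors;
- its own approval or waiver, separate from the carriers' written consent;
- how control mutation status is defined, given that V.4 provides for no testing;
- how the difference in biopsy indication is handled, for example by restricting the comparison to carriers who also had an abnormal PSA or examination;
- the analysis, with a precision or power statement.

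That restriction makes the groups more alike but leaves fewer than 100 carriers if some had normal screening. It also changes the question to detection among men with abnormal screening, so it would not test the incidence part of the hypothesis, which would need rewording. The further costs are approval time, record abstraction and whatever is needed to establish mutation status.
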